3.2 Exclusion Criteria

Subjects should not enter the study if any of the following exclusion criteria are fulfilled:

1. Participation in another clinical study with an investigational product during the last 3 weeks.
2. History of another primary malignancy except for:
 - Malignancy treated with curative intent and with no known active disease \geq 3 years before the first dose of study drug and of low potential risk for recurrence.
 - Adequately treated non-melanoma skin cancer or lentigo maligna without evidence of disease.
 - Adequately treated carcinoma in situ without evidence of disease eg, cervical cancer in situ, in-situ urinary bladder cancer, treated localized prostate cancer and ductal carcinoma-in situ.
 - Indolent hematological malignancies
3. Current or prior use of immunosuppressive medication within 14 days before the first dose of durvalumab, with the exceptions of intranasal, inhaled, topical steroids, or local steroid injections (e.g., intra articular injection), corticosteroids or systemic corticosteroids at physiological doses, which are not to exceed 10 mg/day of prednisone, or an equivalent corticosteroid, and steroids as premedication for hypersensitivity reactions (e.g., CT scan premedication).
4. Any unresolved toxicity (CTCAE grade 2) from therapy for a prior malignancy with the exception of alopecia, vitiligo, and the laboratory values defined in the inclusion criteria.
 - Patients with Grade \geq 2 neuropathy will be evaluated on a case-by-case basis after consultation with the Study Physician.
 - Subjects with irreversible toxicity that is not reasonably expected to be exacerbated by the investigational product may be included (e.g., hearing loss, peripherally neuropathy).
5. Any prior Grade \geq 3 immune-related adverse event (irAE) while receiving any previous immunotherapy agent, or any unresolved irAE >Grade 1.
6. Active or prior documented autoimmune or inflammatory disorders (including inflammatory bowel disease [e.g., colitis or Crohn's disease systemic lupus erythematosus, Sarcoidosis syndrome, or Wegener syndrome [granulomatosis with polyangiitis, Graves' disease, rheumatoid arthritis, hypophysitis, uveitis, etc]). No active diverticulitis within the previous 3 months. The following are exceptions to this criterion:
 - Patients with vitiligo or alopecia
 - Patients with hypothyroidism (e.g., following Hashimoto syndrome) stable on hormone

- replacement
 - Any chronic skin condition that does not require systemic therapy
 - Patients without active disease in the last 5 years may be included but only after consultation with the study physician
 - Patients with celiac disease controlled by diet alone
7. Active or prior documented inflammatory bowel disease (e.g., Crohn's disease, ulcerative colitis).
 8. History of active primary immunodeficiency.
 9. History of allogeneic organ transplant.
 10. History of hypersensitivity to durvalumab or any excipient.
 11. Uncontrolled intercurrent illness including, but not limited to, ongoing or active infection, symptomatic congestive heart failure, uncontrolled hypertension, unstable angina pectoris, cardiac arrhythmia, serious chronic gastrointestinal conditions associated with diarrhea, or psychiatric illness/social situations that would limit compliance with study requirement, substantially increase risk of incurring AEs or compromise the ability of the patient to give written informed consent.
 12. Active infection including tuberculosis (clinical evaluation that includes clinical history, physical examination and radiographic findings, and TB testing in line with local practice), hepatitis B (known positive HBV surface antigen (HBsAg) result), hepatitis C, or human immunodeficiency virus (positive HIV 1/2 antibodies). Patients with a past or resolved HBV infection (defined as the presence of hepatitis B core antibody [anti-HBc] and absence of HBsAg) are eligible. Patients positive for hepatitis C (HCV) antibody are eligible only if polymerase chain reaction is negative for HCV RNA.
 13. History of leptomeningeal carcinomatosis.
 14. Receipt of live attenuated vaccination within 30 days prior to study entry or within 30 days of receiving durvalumab.
 15. Female patients who are pregnant or breastfeeding or male or female patients of reproductive potential who are not willing to employ effective birth control from screening to 90 days after the last dose of durvalumab monotherapy.
 16. Any condition that, in the opinion of the investigator, would interfere with evaluation of study treatment or interpretation of patient safety or study results
 17. Subjects with uncontrolled seizures.
 18. History of interstitial lung disease, idiopathic pulmonary fibrosis, pneumonitis (including drug induced), or evidence of active pneumonitis on screening chest CT scan.
 19. Major surgical procedure within 28 days prior to Cycle 1, Day 1 or anticipation of need for a major surgical procedure during the course of the study.
 20. Receipt of the last dose of therapy (chemotherapy, immunotherapy, endocrine therapy, targeted therapy, biologic therapy, tumor embolization, monoclonal antibodies, or other investigational agent) for an accepted other malignancy as defined in Section 3.3.2 within 30 days prior to the first dose of study drug for lung cancer.
 21. Prior randomisation or treatment in a previous durvalumab clinical study. regardless of treatment arm assignment.

4.0 REGISTRATION AND RANDOMIZATION PROCEDURES

4.1 Registration

Eligible subjects will be identified by the Principal Investigator's and co-investigators' from the Thoracic or Medical Oncology clinics at NYP-Weill Cornell or collaborating institutions. Individuals will be approached and informed of the rationale for the study, investigational nature of the protocol and study drug and the voluntary nature of participation, potential risks and benefits, alternatives to

participation, and study procedures. Individuals will have the opportunity to read the written informed consent document with the understanding that should they decide not to participate, they will still be able to receive any available therapy off-trial. Potential subjects will also have the opportunity to obtain the advice of their treating physician. Investigators or delegates under their direct supervision will verify the subject's understanding of the investigational and voluntary nature of the study, the potential risks and benefits, study procedures, and alternatives prior to signing of the written informed consent. Those who wish to participate in the trial will be required to sign an informed consent form after all their questions are answered. Subjects will be registered to the trial once they have met the eligibility criteria. Documentation of the consent process and that written consent was conducted must be documented in the subject's medical record.

4.2 Randomization

Blocked randomization will be performed for the secondary aim. A series of randomized blocks of 4 will be generated with a 1:1 allocation ratio. This will provide assurance that after four patients are enrolled in the study, there will be two patients assigned to the antibody + radiation arm and two patients assigned to the antibody + no radiation arm. This procedure will allow for a similar number of antibody + radiation patients (Arm 2) and antibody + no radiation patients (Arm 1).

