3.0 PATIENT SELECTION

3.1 Inclusion Criteria

1. Patient has histologically or cytologically proven clinical stages I (tumors > 2 cm), II, and IIIA NSCLC and is considered eligible for surgical resection with curative intent. Patients with 2 primary non-small cell lung cancers are allowed.
2. Measureable disease, as defined by RECIST v1.1.
3. Written informed consent and HIPAA obtained from the subject prior to performing any protocol-related procedures.
4. Age ≥ 18 years at time of study entry
5. Eastern Cooperative Oncology Group (ECOG) performance status of 0 or 1.
6. Adequate normal organ and marrow function as defined below:
 - Haemoglobin ≥ 9.0 g/dL
 - Absolute neutrophil count (ANC) ≥ 1.5 x 10⁹/L (> 1500 per mm³)
 - Platelet count ≥ 100 x 10⁹/L (>100,000 per mm³)
 - Serum bilirubin ≤ 1.5 x institutional upper limit of normal (ULN). This will not apply to subjects with confirmed Gilbert’s syndrome (persistent or recurrent hyperbilirubinemia that is predominantly unconjugated in the absence of hemolysis or hepatic pathology), who will be allowed only in consultation with their physician.
 - AST (SGOT)/ALT (SGPT), and alkaline phosphatase ≤ 2.5 x institutional upper limit of normal (ULN).
 - Serum creatinine CL>30 mL/min by the Cockcroft-Gault formula (Cockcroft and Gault 1976) or by 24-hour urine collection for determination of creatinine clearance:

Males:

$$\text{Creatinine CL (mL/min)} = \frac{\text{Weight (kg)} \times (140 - \text{Age})}{72 \times \text{serum creatinine (mg/dL)}}$$

Females:

$$\text{Creatinine CL (mL/min)} = \frac{\text{Weight (kg)} \times (140 - \text{Age})}{72 \times \text{serum creatinine (mg/dL)}} \times 0.85$$

7. Evidence of post-menopausal status or negative urinary or serum pregnancy test for female pre-menopausal patients. Women will be considered post-menopausal if they have been

amenorrheic for 12 months without an alternative medical cause. The following age-specific requirements apply:

Women <50 years of age would be considered post-menopausal if they have been amenorrheic for 12 months or more following cessation of exogenous hormonal treatments and if they have luteinizing hormone and follicle-stimulating hormone levels in the post-menopausal range for the institution or underwent surgical sterilization (bilateral oophorectomy or hysterectomy).

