5.0 STUDY DESIGN

This is a randomized open label phase II trial of preoperative anti-PD-L1 antibody durvalumab with or without concurrent non-ablative radiation followed by surgical resection and postoperative maintenance durvalumab every 4 weeks for 12 cycles.

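### Section 4.2 prints one fixed, study-wide block size of 4 in an open-label trial, so a recruiter who knows all earlier assignments could deduce on average one third of assignments with certainty

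*Combined protocol and SAP*

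**What the plan says.** Section 4.2 (Randomization) states: "A series of randomized blocks of 4 will be generated with a 1:1 allocation ratio". It adds: "This will provide assurance that after four patients are enrolled in the study", two will be in each arm. That describes one series for the whole study, and no stratification factor or site-level list is named. The stated purpose is comparable arm sizes.

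Section 5.0 says: "This is a randomized open label phase II trial". Arm 2 receives SBRT on days 1 to 3 (Table 1, footnote l), so treating staff can see past assignments.

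Under section 4.1, investigators identify patients from "Thoracic or Medical Oncology clinics at NYP-Weill Cornell or collaborating institutions", and "Subjects will be registered to the trial once they have met the eligibility criteria". Section 4 does not say who holds the list, or that an assignment is released only after registration.

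Section 4.2 opens: "Blocked randomization will be performed for the secondary aim". Sections 1.1 and 11.1.1, however, make the between-arm comparison of pathological response the primary aim.

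**The concern.** When the block size is constant and known, past assignments reveal some of the coming ones. Entry involves some judgement: the patient must be one who "is considered eligible for surgical resection with curative intent" (section 3.1), and section 3.2 has an exclusion that rests on the investigator's opinion. Screening spans days -28 to -1, so the timing of registration also has some room. A recruiter who expects a particular arm could, consciously or not, let that influence who is registered and when.

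At stake is the primary MPR comparison. It depends on assignments that cannot be foreseen at enrolment. Section 11.2.1 plans an unadjusted chi-square or Fisher test and a logistic model with no named covariates, and neither would reveal or remove such a shift. Blinding the radiologists (section 9.2) concerns the reading of clinical response and does nothing at the point of entry.

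**Working it through.** **Plan's own figures.** The documents give none for predictability. The number taken from section 11.1.1 is 30 per arm, 60 in total. Its power statement (0.15 against 0.35, one-sided 0.20, approximately 83%) reproduces at 83.5%.

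**Inputs.** Block size 4, ratio 1:1, one study-wide series (section 4.2); open label (section 5.0); N = 60 = 15 blocks.

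**1. Certain assignments, full knowledge.** A 2 + 2 block has 6 equally likely orders. The 4th assignment is always forced. The 3rd is also forced when the first two match (2 of 6 orders). Forced per block = 1 + 1/3 = 4/3; share = (4/3)/4 = 1/3.

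**2. Spread over 60 patients.** Forced count = 15 + Binomial(15, 1/3): mean 20, SD = √(15 × 1/3 × 2/3) = 1.83, central 95% range 17 to 24. The extremes are 15 and 30, that is 25% to 50% of a list. The chance of more than 20 is 38%.

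**3. Best guess, full knowledge.** The chance of a correct guess at slots 1 to 4 is 1/2, 2/3, 2/3 and 1. Slot 3 is 1/3 × 1 + 2/3 × 1/2 = 2/3. Mean = (17/6)/4 = 17/24 = 70.8%.

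**4. Partial view.** Suppose the recruiter knows the position in the study sequence and sees each earlier assignment in the block with probability s. Slot 3 is certain with probability s²/3. Slot 4 is certain with probability s², because exactly one pair among the first three shares an arm and both of its members must be seen. Share certain = (s²/3 + s²)/4 = s²/3.

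Best guess = [1/2 + (1/2 + s/6) + (1/2 + (1 − (1 − s)²)/6) + (1/2 + (1 − (1 − s)³)/6 + s³/3)]/4.

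| s (assumed) | Certain | Best guess |
|---|---|---|
| 1 | 33.3% | 70.8% |
| 0.75 | 18.8% | 64.6% |
| 0.5 | 8.3% | 59.9% |
| 0.25 | 2.1% | 55.4% |

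**5. Blocks of 4 and 6 in random order.** In 12,000 simulated 60-patient lists, the observer knew the two sizes but not their order and updated on the full history. Certain assignments: 5.5% (about 3 of 60). Best guess: 69.1%. A separate run of 4,000 lists gave 5.6% and 69.1%.

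**6. Arm balance with blocks of 4 and 6.** The mean block is 5 patients, or 2.5 pairs, so patient 60 completes a block with probability about 1/2.5 = 0.4. Otherwise the list stops in a 4-block after 2, a 6-block after 2, or a 6-block after 4, each with probability about 0.2. The chance of imbalance in these states is 1/3, 6/15 and 6/15. Total = 0.2 × (1/3 + 0.4 + 0.4) = 22.7%, which matches the simulation. The imbalance is always 31/29.

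**The case against.** The strongest objection is that the remedy does little against a recruiter who acts on likely as well as certain slots, since the best guess falls only from 70.8% to 69.1%. That stands. The gain is the removal of most certain assignments, not of prediction.

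Full knowledge is also a demanding assumption. Patients may come from several clinics or institutions, and the documents do not say who sees which assignments. Much of eligibility is measurable (histology or cytology, stage, RECIST disease, laboratory limits), and section 4.1 places registration after consent and after the criteria are met. These facts reduce the risk. They do not make release after registration explicit.

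The gain may reach few patients. The protocol cites a July 2019 data cut-off and guidance published in May 2021, so this is a late version, and accrual status is not stated. A fixed block of 4 does meet the stated aim of similar arm sizes, but so do mixed blocks. An unadjusted test that cannot correct steering is also not peculiar to this plan: covariate adjustment would not reliably remove steering on unmeasured factors.

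A reader might infer that the MPR comparison is biased, or that its false-positive rate is inflated by a calculable amount. The documents do not support that. They show no steering, do not link the surgical-eligibility judgement to MPR, and give no basis for a steering size, so any bias or rejection rate would come from an invented input. None is offered here.

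**Conclusion.** The point holds as an avoidable risk, of minor severity. With a known fixed block of 4 and full knowledge of earlier assignments, one third of assignments are certain on average and 70.8% can be guessed. One third is an average and not a ceiling: a single list can run from 25% to 50%. For a recruiter with only a partial view the figures are lower, and the shares seen in the working are assumptions. The enumeration rests only on the block size, the ratio and N = 60.

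The opening words of section 4.2 are a clerical fault in the same paragraph. The randomised comparison serves the primary aim in section 11.1.1 as well as the secondary comparison of clinical response in section 11.1.2.

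**What to change.** For patients still to be randomised, amend section 4.2 as follows:

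- Use 1:1 permuted blocks of randomly varying size, for example 4 and 6, and keep the sizes out of the protocol.
- State that each assignment is released only after the patient has been registered.
- Replace the reference to the secondary aim with the primary MPR comparison.

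The cost is one rewritten paragraph and a new list for the remaining patients. In a full 60-patient list, final arms would be 31/29 instead of 30/30 in about 23% of cases and never further apart. Assignments already made are unaffected.

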5.0 STUDY DESIGN

This is a randomized open label phase II trial of preoperative anti-PD-L1 antibody durvalumab with or without concurrent non-ablative radiation followed by surgical resection and postoperative maintenance durvalumab every 4 weeks for 12 cycles.

5.1 Treatment Plan

Patients with biopsy proven NSCLC clinical stages I (tumors > 2 cm), II, and IIIA will be randomly assigned to 2 preoperative cycles of the anti-PD-L-1 antibody durvalumab followed by surgical resection *or* non-ablative stereotactic radiotherapy given concurrently with the first cycle of the anti-PD-L1 antibody followed by an additional cycle of the antibody alone followed by surgical resection. In both arms of the trial, patients will receive adjuvant durvalumab every 4 weeks for a total of 12 cycles. Patients randomized to the antibody alone arm will receive two cycles of durvalumab at a dose of 1.12 g every three weeks. Patients in the radio-immunotherapy arm will also be treated with two cycles of durvalumab (1.12 g q 3 weeks) plus radiotherapy delivered in 3 daily fraction of 8Gy starting concurrently with the first cycle of durvalumab (see trial schema). This delivered non-ablative radiation dose of 24 Gy is equivalent to a biologically effective dose (BED) of 43.2Gy, which is significantly lower than the standard therapeutic dose for ablation of T1-T2 NSCLC (BED>100Gy). The objective is to induce immunogenic cell death, enhance antigen presentation and increase cytotoxic T lymphocyte activity without tumor ablation. This non-ablative dose of radiation is selected based on the results of studies by one of our co-investigators showing that the 8 Gy_x3 regimen resulted in significant immune modulation in preclinical models (24). A research core biopsy for the collection of tumor tissue is suggested but not mandatory. If a tissue biopsy has already been obtained for diagnostic purposes, a core biopsy may be performed for research purposes only to obtain tumor tissue. If a tissue biopsy has not been performed yet for diagnostic purposes, a core biopsy may be performed for diagnosis and tissue will be obtained for research purposes. Tissue from the preoperative core samples and from the resected surgical specimens will be stored for future correlative studies. Although PDL-1 expression is not required for eligibility, preoperative and post-operative tissue will be stored for future determination of PDL-1 expression. All patients will proceed to surgical resection 2-6 weeks after the second cycle of durvalumab regardless of local response assessment and provided that repeat imaging shows no evidence of systemic disease. Postoperative durvalumab will commence 4-12 weeks postoperatively at a fixed dose of 1.5 g every 4 weeks for 12 cycles. Patients receiving adjuvant chemotherapy may commence adjuvant monthly anti-PD-L1 after completing chemotherapy.

5.2 Limiting normal tissue toxicities with non-ablative SBRT

The thoracic organs that are at risk for radiation injury (i.e., organs at risk [OARs] from non-ablative SBRT doses and are expected to be determinants of toxicity are lung, central airway/bronchi, esophagus, heart, great vessels, spinal cord, and brachial plexus). There is a large body of knowledge on the RT tolerance of those organs to conventionally fractionated RT (1.8-2 Gy per fraction), describing the RT tolerance in terms of volume of the organ irradiated to a certain dose (e.g., V20, volume irradiated to 20 Gy or more) or as mean RT dose to the entire organ. Recently the Task Group 101 (TG-101) of the American Association of Physicists in Medicine (AAPM) has prepared a report to outline the best practice guidelines for SBRT, including protocols, equipment, resources, and quality assurance procedures.⁶ The TG-101 guidelines by the AAPM will be respected. Because the nidus of irradiated tumor and peri-tumoral lung will be removed at the time of surgery, we expect the probability of radiation pneumonitis to be minimal.

- Immobilization: The SBRT frame serves to both immobilize the patient physically and provide an initial approximate target localization, which is refined by in-room image guided techniques. Abdominal compression can be used to minimize respiratory motion, but is not required.
- Simulation imaging: Three-dimensional data sets assembled from 4DCT for visualization and dose calculation for SBRT. CT will be the primary imaging modality for SBRT and will form the basis for treatment calculations. Simulation will take place with the patient in the treatment position. A typical scan should extend at least 5-10 cm (15cm for non-coplanar beams) superior and inferior beyond the treatment field. Along with the target, all OARs should be included and covered by the selected scan length so they can be considered by the treatment planning software and evaluated with dose-volume histograms. For SBRT applications, tomographic slice thickness of 1-3 mm will be used.
- Data acquisition for mobile lung tumors and respiratory motion management: Techniques to image moving targets include slow CT, breath-hold techniques, gated approaches, 4DCT used in conjunction with maximum-intensity projection, minimum-intensity projection, and respiration-correlated PET-CT.
- Treatment planning: Planning will make use of the ICRU 50 and 62 definitions for gross tumor volume (GTV), clinical tumor volume (CTV), planning target volume (PTV) and OAR. With SBRT the GTV and CTV are considered identical. The PTV addresses all the possible geometrical variations by adding a variable margin for setup uncertainties, machine tolerances, and intratreatment variations to the CTV. By using the 4DCT to treatment planning the CTV to PTV expansion will be 0.5 cm in all directions.
- Dose constraints: Dose constraints for OARs published by the TG-101 AAPM report will be respected.
- Image-guided localization: Volumetric image guidance will allow for the precise localization of bone and soft tissue targets. This will be achieved with MV or kV cone beam scanning.

5.3 Duration of follow-up

Post-operatively, patients will be followed monthly from the date of the last infusion dose until month 4, at month 6, and subsequently every 6 months for 2 years. Patients removed from the study for unacceptable adverse events will be followed until resolution or stabilization of the adverse event. Follow-up imaging will be performed by CT scan every 6 months for 2 years. Recurrent disease should be pathologically confirmed whenever possible.

